9.3.3.2 Analysis Method

Absolute change from baseline in BMI z-score at Week 24 (for subjects ≤ 20 years of age at Baseline): Analysis of this variable will be based on an MMRM similar to the analysis of the primary efficacy variable, excluding the covariate of age at screening (<18 versus ≥ 18 years of age), for subjects ≤ 20 years of age at Baseline. Data obtained from Day 15, Week 4, Week 8, Week 16, and Week 24 Visits will be included in the model. Plot and summary tables similar to those for ppFEV₁ and SwCl will be provided.

Absolute change from baseline in Weight z-score at Week 24 (for subjects ≤ 20 years of age at Baseline): Analysis of this variable will be based on an MMRM similar to the analysis of the primary efficacy variable, excluding the covariate of age at screening (<18 versus ≥ 18 years of age), for subjects ≤ 20 years of age at Baseline. Data obtained from Day 15, Week 4, Week 8, Week 16, and Week 24 Visits will be included in the model. Plot and summary tables similar to those for ppFEV₁ and SwCl will be provided.

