8.1 Inclusion Criteria

- 1. Subject (or the subject's legally appointed and authorized representative) will sign and date an informed consent form (ICF) and, when appropriate, an assent form.
- 2. Willing and able to comply with scheduled visits, treatment plan, study restrictions, laboratory tests, contraceptive guidelines (as applicable), and other study procedures.
 - For subjects <18 years of age: as judged by the investigator, parent or legal guardian must be able to understand protocol requirements, restrictions, and instructions and the parent or legal guardian should be able to ensure that the subject will comply with and is likely to complete the study as planned.
- 3. Subjects (male or female) 6 years of age and older on the date of informed consent.
- 4. Subjects has an eligible ELX/TEZ/IVA-responsive *CFTR* mutation listed in Table 15-1 and none of the exclusionary mutations in Table 15-2.
- 5. Subject has stable CF disease, as deemed by the investigator, before randomization.
- 6. Forced expiratory volume in 1 second (FEV₁) value ≥40% and ≤100% of predicted mean for age, sex, and height (equations of the Global Lung Function Initiative [GLI])¹¹ at the Screening Visit (spirometry measurements must meet American Thoracic Society/European Respiratory Society criteria¹² for acceptability and repeatability).
- 7. Subject is able to swallow tablets.

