7.3 Randomization

Subjects will be randomized 2:1 (ELX/TEZ/IVA group: placebo group). Randomization will be stratified based on ppFEV₁ determined during the Screening Period (<70 versus \geq 70), age at the Screening Visit (<18 years old versus \geq 18 years old) and *CFTR* mutation group (contains \geq 1 RF-like mutation versus does not contain an RF-like mutation).

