9.3.1.2 Primary Analysis

The primary analysis will be performed using a MMRM with change from baseline at Day 15, Week 4, Week 8, Week 16, and Week 24 as the dependent variable. The model will include treatment group, visit, and treatment by visit interaction as fixed effects, with continuous baseline ppFEV₁, age at screening (<18 versus \geq 18 years of age) and mutation group (contains \geq 1 RF-like mutation versus does not contain an RF-like mutation) as covariates. The model will be estimated using restricted maximum likelihood. Denominator degrees of freedom for the *F*-test for fixed effects will be estimated using the Kenward-Roger approximation². An unstructured covariance structure will be used to model the within-subject errors. If the model estimation does not converge, a compound symmetry covariance structure will be used instead. Conditional on the observed data and covariates, missing data will be assumed to be missing at random.

The primary result obtained from the model will be the estimated treatment difference through Week 24, defined as the averaged treatment effects estimated at Week 4, Week 8, Week 16, and Week 24. The adjusted means with 2-sided 95% CIs and 2-sided *P* value will be provided. Furthermore, the treatment difference at each post-baseline visit obtained from the model will also be provided.

The estimated within group change from baseline and treatment difference at each post-baseline visit, obtained from the model, will be provided. The estimated within group change and its SE at each post-baseline visit will also be plotted by treatment group. In addition, the post-baseline raw values and the absolute change from baseline at each post-baseline visit will be summarized descriptively (n, mean, SD, median, minimum, and maximum).

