9.3.1.5 Subgroup Analysis

Subgroup analyses of the primary efficacy endpoint will be performed using a model similar to that of the primary analysis for each of the following subgroups.

- Age at Screening (<18, \geq 18 years)
- ppFEV₁ at baseline (< 70, \geq 70)
- Sex (male, female)

The MMRM used for the primary analysis will be used for the subgroup analysis, where the same model will be applied to each category of the subgroup. Note that for the subgroup analysis based on age, the covariate of age at screening (<18 versus \geq 18 years of age) from the MMRM will be removed. The adjusted means with 2-sided 95% CIs will be provided. Furthermore, estimated between group difference through Week 24 within a subgroup will also be presented in a forest plot. Note: Due to potential small sample size, the results from above mentioned subgroup analysis should be interpreted with caution.

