9.3.3 Analysis of Other Endpoints

9.3.3.1 Definition of Variables

BMI z-score: the BMI score, adjusted for age and sex, will be referred to as BMI-for-age z-score (BMI z-score). The BMI z-score will be calculated by using Centers for Disease Control and Prevention (CDC) growth charts⁷, with the age (in months) used for the calculation defined in [Appendix A](#).

Weight z-score: weight, adjusted for age and sex, will be referred to as weight-for-age z-score (Weight z-score). The Weight z-score will be calculated by using Centers for Disease Control and Prevention (CDC) growth charts⁷, with the age (in months) used for the calculation defined in [Appendix A](#).

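### The BMI and weight z-score models drop the age stratification factor although it can be estimated in subjects aged 20 or under; keeping it is a free, minor improvement

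*SAP*

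**What the plan says.** SAP section 7.3 stratifies randomisation by three factors: "Randomization will be stratified based on ppFEV₁ determined during the Screening Period", CFTR mutation group, and "age at the Screening Visit (<18 years old versus" 18 or over). The primary MMRM in SAP section 9.3.1.2 carries these through as covariates, "with continuous baseline ppFEV₁, age at screening" in two categories, and mutation group.

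SAP section 9.3.3.2 analyses change in BMI z-score and in weight z-score at Week 24 in subjects aged 20 or under at baseline. Each model is described as similar to the primary one, "excluding the covariate of age at screening". No reason is given.

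The only other place where the SAP removes this factor is section 9.3.1.5: "Note that for the subgroup analysis based on age, the covariate of age at screening" is taken out of the model.

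The protocol (section 12.3.3.3) leaves the z-score analysis details to the SAP, so the two documents do not conflict.

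**The concern.** In the age subgroup analysis the factor has to go, because it is constant within each subgroup. That reason does not carry over to the z-score analyses. The protocol admits subjects from 6 years of age (section 8.1), so a set cut at 20 years contains both 6-17-year-olds and 18-20-year-olds, and the factor takes both values.

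A z-score places a child's BMI or weight against a reference for age and sex. It does not ensure that the change over 24 weeks is the same in growing children as in 18-20-year-olds. If mean change differs between the two groups, leaving the factor out moves that difference into the residual variance and the standard error is slightly too large. The z-score models would also use a different covariate set from the raw BMI and weight models in SAP section 9.3.2.2, for which no exclusion is stated.

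**Working it through.** **What the documents supply.** They give no SD, sample size or power for the z-scores. The only power statement is for ppFEV₁ (SAP section 7.2). With 10% dropout the arms are 162 and 81, and the noncentrality is 4/(9·√(1/162 + 1/81)) = 4/1.225 = 3.27. A two-sided t-test at 0.05 then has 90.2% power, against about 90% stated. That figure reproduces, but it does not bear on this point.

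**Is the factor estimable?** Four places in the SAP, side by side:

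| Analysis | Ages included | Outcome age-standardised? | Age factor |
|---|---|---|---|
| ppFEV₁, primary (9.3.1.2) | 6 and over | Yes, GLI equations with age as an input (Appendices A and C) | Kept |
| ppFEV₁ by age subgroup (9.3.1.5) | <18, or ≥18 | Yes | Dropped; constant |
| Raw BMI and weight (9.3.2.2) | 6 and over | No | No exclusion stated |
| BMI and weight z-score (9.3.3.2) | 6-20 | Yes, CDC charts (9.3.3.1) | Dropped; not constant |

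**Effect on the standard error.** Let f be the share of the subset aged 18-20, d the difference between strata in mean z-score change, and s the residual SD with the factor in the model. The ratio of explained to residual variance is r = f(1−f)d²/s². Omitting the factor multiplies the standard error by about √(1+r). The inputs are assumptions: f = 0.10-0.25, d = 0-0.15 z, s = 0.3.

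- d = 0: r = 0, no loss.
- f = 0.10, d = 0.05: r = 0.09 × 0.0025/0.09 = 0.0025; √1.0025 − 1 = 0.1%.
- f = 0.25, d = 0.15: r = 0.1875 × 0.0225/0.09 = 0.0469; √1.0469 − 1 = 2.3%.

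On a wider grid (f = 5-30%), the standard error is 0.1-0.4% larger for d = 0.2 residual SDs, 0.6-2.6% for 0.5 SDs and 1.5-6.5% for 0.8 SDs. The upper assumed case above is 0.15/0.3 = 0.5 SDs, so 0.8 lies outside the assumed range.

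**Simulation check.** This used a single-visit linear model with 90 subjects (assumed), 2:1 allocation and 4,000 runs. The under-18s were allocated in balanced blocks and the 18-20-year-olds independently. The true effect for power was 0.65 SD.

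| f, d (SDs) | Type I error without / with age | Power without / with age |
|---|---|---|
| 0.2, 0.2 | 5.1% / 5.0% | 82.1% / 81.8% |
| 0.2, 0.5 | 4.5% / 4.8% | 80.1% / 80.6% |
| 0.3, 0.8 | 4.5% / 4.6% | 77.5% / 82.1% |

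Mean estimates were close to the true effect with and without the factor. The first two power differences (0.3 and 0.5 points) are within simulation error, about √(0.8 × 0.2/4000) = 0.6 points per entry. Only the third row, outside the assumed range, shows a clear gain.

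**Chance imbalance.** Subjects aged 18-20 are a slice of the ≥18 stratum. Stratification balances that stratum, not the slice, so 2:1 is not guaranteed within it. In a given trial the unadjusted estimate moves by d times the difference between arms in the share aged 18-20. This averages to zero over randomisations, and the factor removes it.

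**The case against.** The strongest defence is in SAP section 9.3.3.1: "the BMI score, adjusted for age and sex, will be referred to as BMI-for-age z-score", and weight is treated the same way, with age in months recomputed at each visit (Appendix A). Dropping a two-level age term when the outcome is already standardised month by month is a coherent, prespecified choice, and it fits the pattern that age is excluded from these two z-score models while no exclusion is stated for raw BMI and weight. A reader might therefore go too far in calling the exclusion needless or an oversight. The documents do not support that, because a plausible motive is there even though it is unstated.

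The motive is not decisive. Percent predicted FEV₁ is also computed with age as an input, and the SAP keeps the factor there. The parallel is imperfect, since the primary analysis covers all adults and the factor may have more to explain. But it shows that age-standardising an outcome is not, in this SAP, sufficient reason to drop the factor.

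Two more objections stand in full. Nothing in the documents shows that mean z-score change differs between the strata, so the loss may be zero. And restoring the term would not make this subset reproduce the randomisation strata, because the cut at 20 years takes only part of the ≥18 stratum. A reader might infer that the analysis is invalid because it departs from the randomisation. It is not: omitting the factor costs a little precision, and any error in the test tends to be conservative.

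**Conclusion.** The point holds as a minor, free improvement. A randomisation factor that can be estimated in the z-score population is left out of two models without a stated reason. Under the assumptions set out above, the standard error is about 0-2.3% larger as a result; the lower end applies if age-standardised change does not differ between the strata. Bias and type I error are not materially affected.

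A reader might also infer that the BMI and weight results are at risk. They are not. The z-scores are listed as other endpoints (SAP section 6.3) and are outside the testing hierarchy (section 9.3.2.3). The formally tested raw BMI and weight analyses have no such exclusion. No primary or secondary conclusion depends on this choice.

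**What to change.** In SAP section 9.3.3.2, delete the clause "excluding the covariate of age at screening", with its bracketed age categories, from both the BMI z-score and the weight z-score paragraphs, and keep the <18 versus ≥18 covariate as in the primary model. The cost is one degree of freedom in each model and an edit to two sentences, made by SAP amendment before data lock. If the sponsor prefers to leave age out, one sentence giving the reason would close the gap.

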9.3.4 Analysis of Additional Efficacy Variables

9.3.4.1 Analysis of Additional Spirometry Variables

Summary statistics for raw values and for changes from baseline of the following spirometry measurements will be presented by treatment group at each visit:

- FEV₁:
 - Absolute change from baseline in FEV₁ (L)
 - Relative change from baseline in FEV₁ (%)
 - Absolute change from baseline in percent predicted FEV₁ (percentage points)
 - Relative change from baseline in percent predicted FEV₁ (%)
- FVC:
 - Absolute change from baseline in FVC (L)
 - Relative change from baseline in FVC (%)
 - Absolute change from baseline in percent predicted FVC (percentage points)
 - Relative change from baseline in percent predicted FVC (%)

- $\text{FEF}_{25-75\%}$:
 - Absolute change from baseline in $\text{FEF}_{25-75\%}$ (L/sec)
 - Relative change from baseline in $\text{FEF}_{25-75\%}$ (%)
 - Absolute change from baseline in percent predicted $\text{FEF}_{25-75\%}$ (percentage points)
 - Relative change from baseline in percent predicted $\text{FEF}_{25-75\%}$ (%)
- FEV_1/FVC :
 - Absolute change from baseline in FEV_1/FVC
 - Relative change from baseline in FEV_1/FVC (%)
 - Absolute change from baseline in percent predicted FEV_1/FVC
 - Relative change from baseline in percent predicted FEV_1/FVC (%)

9.3.4.2 Analysis of Other CFQ-R Variables

Absolute change in the CFQ-R non-respiratory domain score from baseline through Week 24:

Analysis of this domain(s) will be based on an MMRM similar to the analysis of the primary efficacy variable. Data obtained from Week 4, Week 8, Week 16, and Week 24 Visit will be included in the model and all these visits will be included in the estimation of the average treatment effect through Week 24. Summary tables similar to those for ppFEV₁ and SwCl will be provided.

9.3.5 Additional Analysis

For all subjects (pooled together) with any of these mutations 2789+5G>A, 3272-26A>G, and 3849+10kbC>T, the absolute change from baseline through Week 24 in the following efficacy endpoints:

- ppFEV₁
- SwCl
- CFQ-R RD

will be summarized descriptively (n, mean, SD, median, minimum, maximum, and 95% CI). These analyses will also be conducted for all subjects (pooled together) with any of these mutations: P5L, R117C, L206W, V232D, T338I, R347H, A455E, S945L, L997F, R1066H, D1152H, G85E, R347P, L1077P, and M1101K.

9.3.6 Remote Measures in Extenuating Circumstances

CSP Section 9.1.7 states that, under extenuating circumstances, remote measures may be implemented (e.g., if a subject is unable to travel to the study site due to safety concerns and/or local restrictions related to COVID-19 or other emerging events). Such measures, pertaining to spirometry, will be listed if available.

9.4 Safety Analysis

All safety analyses will be based on data from the TE period. Subjects will be analyzed according to the treatment they received in the Treatment Period. For subjects receiving study drug from more than one treatment group, the treatment group allocation will ELX/TEZ/IVA.

The overall safety profile of the study drug will be assessed in terms of the following safety and tolerability endpoints:

- TEAEs
- Clinical laboratory values
- ECGs
- Vital signs
- Pulse oximetry
- Ophthalmologic examination

Only descriptive analysis of safety will be performed. No statistical testing will be performed.

9.4.1 Adverse Events

For analysis purposes, AEs will be classified as pretreatment AEs, TEAEs, or post-treatment AEs, defined as follows:

Pretreatment AE: any AE that occurred before the first dose date of study drug

TEAE: any AE that worsened (either in severity or seriousness) or that was newly developed on or after the first dose date of study drug through the end of the TE period

Post-treatment AE: any AE that worsened (either in severity or seriousness) or that was newly developed after the TE period

For AEs with completely missing or partially missing start dates, if there is no clear evidence that the AEs started before or after study treatment, the AEs will be classified as TEAEs.

Details for imputing missing or partial start dates of AEs are described in [Appendix E](#).

An overview of all TEAEs by treatment group and overall will be summarized in the following categories:

- Number of TEAEs (total number of TEAEs only)
- Subjects with any TEAEs
- Subjects with TEAEs by strongest relationship
- Subjects with TEAEs by maximum severity
- Subjects with TEAEs leading to study drug discontinuation (discontinuation of any study drug)
- Subjects with TEAEs leading to study drug interruption (interruption of any study drug)
- Subjects with Grade 3/4/5 TEAEs
- Subjects with related TEAEs
- Subjects with serious TEAEs
- Subjects with related serious TEAEs
- Subjects with TEAE leading to death

The following summary tables of TEAEs will be presented by treatment group:

- All TEAEs
- Grade 3/4/5 TEAEs
- TEAEs by strongest relationship
- TEAEs by maximum severity
- TEAEs leading to treatment discontinuation
- TEAEs leading to treatment interruption
- Related TEAEs
- Serious TEAEs
- Related serious TEAEs
- TEAEs leading to death

Summaries will be presented by MedDRA SOC and PT using frequency counts and percentages (i.e., number and percentage of subjects with an event). When summarizing the number and percentages of subjects, subjects with multiple occurrences of the same adverse event or a continuing adverse event will be counted once, and only the maximum severity level will be presented in the severity summaries, and the strongest relationship level in the relationship summaries.

Additional summary tables will be presented by treatment for TEAEs showing number and percentage of subjects

- All TEAEs by PT
- All Related TEAEs by PT

All AEs, including pretreatment AEs, TEAEs, and post-treatment AEs, will be presented in an individual subject data listing based on the All Subjects Set. In addition, a listing containing individual subject adverse event data for TEAEs leading to treatment discontinuation, TEAEs leading to treatment interruption, Grade 3/4/5 TEAEs, SAEs and all deaths will be provided separately, with a flag indicating the TEAE status for SAEs and deaths.

9.4.2 Clinical Laboratory

For the treatment-emergent laboratory assessments, the observed values and change from baseline values of the continuous hematology, coagulation, and chemistry results will be summarized in SI units at each visit by treatment group.

The number and percentage of subjects meeting at least 1 threshold analysis criterion event during the TE period will be summarized by treatment group. The threshold analysis criterion shift from baseline will also be summarized for selected laboratory parameters. The threshold analysis criteria are provided in [Appendix F](#).

For select LFT laboratory tests (ALT, AST, ALP, and total bilirubin), a scatter plot of the maximum treatment-emergent value versus the baseline value corresponding to \times ULN will be presented. Further, a scatter plot of the maximum treatment-emergent value of ALT and AST,

separately, versus the maximum treatment-emergent value of total bilirubin corresponding to \times ULN will also be presented by treatment group.

Results of positive urine/serum pregnancy test will be listed in individual subject data listings only. For positive serum pregnancy listing, subjects with serum hCG above the upper limit of normal will be selected.

In addition, a listing containing individual subject hematology, chemistry, and coagulation values will be provided. This listing will include data from both scheduled and unscheduled visits.

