9.9.1 Liver Function Tests

The central laboratory will notify the medical monitor of ALT or AST $>3 \times$ ULN and total bilirubin $>2 \times$ ULN that are derived from centrally submitted samples.

Subjects with new treatment-emergent ALT or AST elevations of $>3 \times ULN$, with or without total bilirubin $>2 \times ULN$, must be followed closely, including confirmatory testing performed by the central laboratory within 48 to 72 hours of the initial finding and subsequent close monitoring of ALT, AST, and bilirubin levels, as clinically indicated.

If a subject cannot return to the site for confirmatory testing, a local laboratory may be used. Local laboratory results must be reported immediately to the medical monitor, and the subject must have the tests repeated and sent to the central laboratory as soon as possible (ideally within 48 to 72 hours).

Study drug administration must be interrupted immediately (prior to confirmatory testing) if any of the following criteria are met:

- ALT or AST >8 × ULN
- ALT or AST >5 × ULN for more than 2 weeks
- ALT or AST >3 × ULN, in association with total bilirubin >2 × ULN and/or clinical jaundice

A thorough investigation of potential causes should be conducted, and the subject should be followed closely for clinical progression.

Study drug administration **must be discontinued** if the following criterion is met:

• Subsequent ALT or AST values confirm the initial elevation that satisfied the interruption rule (above), and no convincing alternative etiology (e.g., acetaminophen use, viral hepatitis, alcohol ingestion) is identified, regardless of whether transaminase levels have improved.

All subjects in whom treatment is discontinued for elevated transaminases (and bilirubin, as applicable) should have these levels monitored closely until levels normalize or return to baseline.

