Appendix F: Criteria for Threshold Analysis

Table 12-3 Threshold Analysis Criteria for Laboratory Tests (as applicable)

Parameter	Threshold Analysis	Comments
Clinical Chemistry (LFT)		
ALT	>ULN - \leq 3xULN >3x - \leq 5xULN >5x - \leq 8xULN >8x - \leq 20.0xULN >20.0xULN	FDA DILI Guidance Jul 2009.
AST	>ULN - \leq 3xULN >3x - \leq 5xULN >5x - \leq 8xULN >8x - \leq 20.0xULN >20.0xULN	FDA DILI Guidance Jul 2009.
ALT or AST	(ALT>ULN - \leq 3xULN) or (AST>ULN - \leq 3xULN) (ALT>3x - \leq 5xULN) or (AST>3x - \leq 5xULN) (ALT>5x - \leq 8xULN) or (AST>5x - \leq 8xULN) (ALT>8x - \leq 20xULN) or (AST>8x - \leq 20xULN) ALT>20xULN or AST> 20xULN	FDA DILI Guidance
Alkaline Phosphatase	>ULN - \leq 1.5xULN >1.5 - \leq 2.5xULN >2.5 - \leq 5.0xULN >5.0 - \leq 20.0xULN >20.0 x ULN	FDA DILI Guidance Jul 2009.
Total Bilirubin	>ULN - \leq 1.5xULN >1.5 - \leq 2xULN >2 - \leq 3xULN >3 - \leq 10xULN >10xULN	FDA DILI Guidance Jul 2009.
Direct Bilirubin	>ULN - \leq 1.5xULN >1.5 - \leq 2xULN >2 - \leq 3xULN >3 - \leq 10xULN >10xULN	FDA DILI Guidance Jul 2009.
ALT and Total Bilirubin	ALT>3xULN and TBILI>2xULN	FDA DILI Guidance Jul 2009.
AST and Total Bilirubin	AST>3xULN and TBILI>2xULN	FDA DILI Guidance Jul 2009.
(ALT or AST) and Total Bilirubin	(ALT>3xULN or AST>3xULN) and TBILI>2xULN	FDA DILI Guidance Jul 2009.

Table 12-3 Threshold Analysis Criteria for Laboratory Tests (as applicable)

Parameter	Threshold Analysis	Comments
GGT	>ULN - \leq 2.5xULN >2.5 - \leq 5.0xULN >5.0 - \leq 20.0xULN >20.0xULN	CTCAE grade 1-4
Clinical Chemistry (NON-LFT)		
Albumin	<LLN - \geq 30 g/L <30 - \geq 20 g/L <20 g/L	CTCAE grade 1-3
Amylase	>ULN - \leq 1.5xULN >1.5x - \leq 2xULN >2x - \leq 5xULN >5xULN	Criteria based upon CTCAE
Creatinine	>ULN - \leq 1.5xULN >1.5 - \leq 3.0xULN >3.0 - \leq 6.0xULN >6.0xULN	CTCAE grades 1-4
Lipase	>ULN - \leq 1.5xULN >1.5x - \leq 2xULN >2x - \leq 5xULN >5xULN	Criteria based upon CTCAE
Total protein	<LLN >ULN	No CTCAE
Creatine Kinase	>ULN - \leq 2.5 x ULN >2.5 - \leq 5 x ULN >5 - \leq 10x ULN >10 x ULN	CTCAE grades 1-4
Hematology		
Hemoglobin	Hgb decreased (anemia) <LLN - \geq 100 g/L <100 - \geq 80 g/L < 80 g/L Hgb increased >ULN - \leq 20 g/L above ULN >20 g/L above ULN - \leq 40 g/L above ULN >40 g/L above ULN	CTCAE grade 1-3 CTCAE grade 1-3
Platelets	Platelet decreased <LLN - \geq 75.0 x 10e9 /L <75.0 - \geq 50.0 x 10e9 /L <50.0 - \geq 25.0 x 10e9 /L <25.0 x 10e9 /L Platelet increased >ULN	CTCAE grade 1-4 No CTCAE available

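### SAP Table 12-3 joins ALT and AST bands with 'or', so a subject whose two peaks lie in different bands counts twice and the combined number above 3, 5 or 8 × ULN can only be bounded (minor)

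*SAP*

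**What the plan says.** SAP section 9.4.2 gives the counting rule for laboratory thresholds: "The number and percentage of subjects meeting at least 1 threshold analysis criterion event during the TE period will be summarized by treatment group". The criteria are in Appendix F, Table 12-3.

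- **ALT alone and AST alone:** five bands that do not overlap. The first runs from above ULN to 3 × ULN, and the rest are ">3x - \leq 5xULN >5x - \leq 8xULN >8x - \leq 20.0xULN >20.0xULN".
- **ALT or AST combined:** the same five bands, each met if either enzyme lies in it. The second, for example, is "ALT>3x - \leq 5xULN) or (AST>3x - \leq 5xULN".
- **Open-ended transaminase rows:** for the combined criterion, only "ALT>20xULN or AST> 20xULN". Rows above 3 × ULN without an upper limit exist only jointly with bilirubin, as in "ALT>3xULN or AST>3xULN) and TBILI>2xULN".

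Protocol section 9.9.1 works with open-ended limits. A new elevation above 3 × ULN, with or without raised bilirubin, leads to close follow-up, "including confirmatory testing performed by the central laboratory within 48 to 72 hours of the initial finding and subsequent close monitoring". One of the interruption criteria is simply "ALT or AST >8 × ULN".

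**The concern.** A table of closed bands gives the number of subjects above a cut-off only if each subject sits in exactly one band. Only then do the bands above the cut-off add up to the right count. The combined rows break this by construction, because ALT and AST can peak in different bands. The single-enzyme rows may break it too, because the laboratory text does not say that a subject is classified by the worst value.

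Elevated transaminases are an event of special interest in SAP section 9.4.9.1, and the natural questions of this table are how many subjects in each arm went above 3, 5 or 8 × ULN. There is no row for any of these. A reader who adds the bands will count some subjects twice, and nothing in the output shows how many.

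**Working it through.** No stated figure in the plan has to be reproduced; the question is one of counting logic. The check applies the Table 12-3 bands to three constructed subjects. The values, in × ULN over five visits, are assumptions chosen to show the mechanism. They do not predict the trial's data.

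| Subject | ALT | AST |
|---|---|---|
| A | 2.1, 4.2, 9.0, 6.0, 2.5 | 1.5, 3.4, 5.5, 4.0, 1.2 |
| B | 0.8, 3.5, 1.4, 0.9, 0.9 | 0.7, 6.0, 2.0, 0.8, 0.8 |
| C | 0.9, 1.2, 3.3, 1.1, 0.9 | 0.8, 0.9, 1.5, 1.0, 0.9 |

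**True combined counts.** The larger of the two peaks is 9.0 for A, 6.0 for B and 3.3 for C. So 3 subjects exceed 3 × ULN, 2 exceed 5 and 1 exceeds 8.

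**Combined rows, each enzyme's maximum only.** A falls in >8–20 (ALT 9.0) and >5–8 (AST 5.5). B falls in >3–5 (ALT 3.5) and >5–8 (AST 6.0). C falls in >3–5 (ALT 3.3) and >1–3 (AST 1.5).

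| Band | >1–3 | >3–5 | >5–8 | >8–20 | >20 |
|---|---|---|---|---|---|
| Subjects | 1 | 2 | 2 | 1 | 0 |

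Sums of bands: above 3, 2 + 2 + 1 + 0 = 5 (true 3); above 5, 2 + 1 + 0 = 3 (true 2); above 8, 1 + 0 = 1 (true 1).

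**Combined rows, every value counted.** The bands become 3, 3, 2, 1, 0. The sums are 6, 3 and 1 against a true 3, 2 and 1.

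**ALT alone.** With every value counted, the bands are 3, 3, 1, 1, 0. They sum to 5, 2 and 1 above 3, 5 and 8, against a true 3, 1 and 1. With the maximum only, the bands are 0, 2, 0, 1, 0 and the sums are 3, 1 and 1, which is correct. A maximum rule therefore cures the single-enzyme rows and leaves the combined rows wrong.

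**What the combined rows do determine.** Let b₁, b₂, … be the band counts above a cut-off and N the number of subjects above it. Everyone in a band is above the cut-off, and everyone above it is in at least one band, so max(bᵢ) ≤ N ≤ Σbᵢ. Under the per-enzyme maximum this gives 2 ≤ N ≤ 5 above 3 × ULN and 2 ≤ N ≤ 3 above 5 × ULN. The bounds meet only when a single band above the cut-off is occupied, as above 8 × ULN here. The ALT row raises the lower limit above 3 × ULN to 3, but the upper limit stays at 5 (3 with ALT plus 2 with AST).

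**Is a one-band rule stated elsewhere?** The SAP writes such rules for other outputs: maximum severity for adverse events (9.4.1) and lowest oxygen saturation (9.4.5). None is written for laboratory thresholds.

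**The case against.** The strongest reply is that a reader might infer from section 9.4.2 that subjects are counted in every band they touch, and the SAP does not say that. Non-overlapping bands suit a worst-value classification. SAP section 9.1 brings unscheduled values into treatment-emergent maxima and minima for safety analyses, which favours that reading without stating it. The instruction to use all reported values for threshold purposes (Appendix A, derived variables) concerns ECGs only. Section 9.1 also refers to an internal document of programming rules that is not available here. All of this stands, and it is why the single-enzyme rows are only a gap in wording. It does not rescue the combined rows, which double count even with per-enzyme maxima.

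Three further inferences go beyond the documents.

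- **A fixed inflation factor from repeat testing.** Section 9.9.1 requires confirmation within 48 to 72 hours and then monitoring as clinically indicated. Weekly tests for 4 weeks apply only after study drug is resumed. Any average number of bands per subject would rest on assumed decline curves and an assumed retest schedule.
- **Unequal distortion between arms.** The retest rule is the same for all blinded subjects, and nothing in the documents shows a differential effect.
- **That the missing rows are exactly the protocol's interruption limits.** Only the limit of 8 × ULN is plain. The 5 × ULN limit carries a duration of more than 2 weeks. The 3 × ULN limit requires bilirubin above 2 × ULN and/or jaundice, and its bilirubin part already has an open-ended row.

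It is also fair to say that the information is not lost. Section 9.4.2 plans scatter plots of maximum ALT and AST, a shift summary for selected parameters and full listings, and section 9.4.9.1 summarises transaminase events by preferred term. None of these is specified to give counts above 3, 5 or 8 × ULN.

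**Conclusion.** The point holds for the combined ALT-or-AST rows and does not depend on how the single-enzyme rows are programmed. A subject whose ALT and AST peaks lie in different bands is counted in two rows, and the number above 3, 5 or 8 × ULN is only bounded. For ALT and AST alone the finding is narrower: no worst-value rule is stated, and an unwritten maximum-value convention would make those rows correct.

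Summing the bands can never understate the count, and it overstates it whenever a subject enters two bands above the cut-off. How far depends on the data, so no figure should be quoted; the three-subject example shows direction only. Severity is minor: safety is descriptive without testing, the data are retained, and the incidence of the event of special interest does not come from this table.

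**What to change.** In SAP section 9.4.2 and Table 12-3:

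1. State that each subject is classified once per parameter, by the maximum treatment-emergent value, scheduled or unscheduled.
2. For the combined rows, classify by the larger of ALT/ULN and AST/ULN over the treatment-emergent period.
3. Show cumulative rows above 3, 5, 8 and 20 × ULN for ALT, AST and ALT-or-AST. The row above 20 is already open-ended. Once steps 1 and 2 are in place, the others are sums of bands and mainly spare the reader the addition.

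In the example, steps 1 and 2 give 3, 2 and 1 subjects above 3, 5 and 8 × ULN, which match the true counts. The cost is SAP wording and minor table programming, with no new data.
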